### 1.2.1.2 Safety

To date, balovaptan has been dosed to 294 healthy subjects in 10 completed or clinically complete, reporting ongoing Phase 1 studies (Studies BP25694, BP28318, BP28977, BP29279, BP29412, WP40038, WP40608, WP40609, WP40607, WP40734).

Additionally, balovaptan was investigated in a completed Phase 2 study in 148 adult male patients with ASD (BP28420, "VANILLA"), about 30 of whom received 10 mg qd for 12 weeks.

Balovaptan has been found to be safe and well tolerated in clinical trials. No particular safety concerns have emerged, and no adverse drug reactions have been identified per reference safety information (Section 6.4 of the IB). The maximum tolerated dose was not reached in either the single ascending dose (SAD) study with single doses (up to 76 mg) or the multiple ascending dose (MAD) study with multiple doses (up to 52 mg qd for 14 days) in healthy subjects. [REDACTED]

[REDACTED]

Balovaptan has been found to be safe and well tolerated in male patients with ASD at doses up to 10 mg/day (highest dose administered) for a period of 12 weeks (Study BP28420). No particular safety patterns attributable to the administration of balovaptan were identified. [REDACTED]

[REDACTED]

[REDACTED]

[REDACTED]

[REDACTED]

Refer to the IB for more details on non-clinical and clinical studies.

### **1.3 STUDY RATIONALE AND BENEFIT-RISK ASSESSMENT**

This study will investigate the effect of esomeprazole and the effect of food on the PK of balovaptan in healthy volunteers. Balovaptan has shown pH dependent solubility, which may affect its absorption at values closer to neutral pH. The 20 mg tablet used in this study is the highest possible dose strength of the to-be-marketed formulation.

The study will be performed in healthy subjects who will not receive any health benefit from participating in this study. The study is necessary for the further development of balovaptan and may be of benefit for future patients.

The balovaptan dose planned for this study is 20 mg with a single tablet of the highest dose strength of the final formulation that may be used in pivotal studies. Plasma exposures with a single dose of balovaptan 20 mg are predicted to be approximately 8-fold below the concentrations observed after the once daily balovaptan doses for 14 days in Study BP25694 (52 mg qd) and Studies WP40607 and WP40734 (50 mg qd; both studies are clinically completed but have not yet reported). The SAD part in the entry-into-human study (BP25694) applied single doses up to 76 mg. No safety concern for the administration of a single dose of 20 mg have emerged from these trials or from any other clinical trial.

Esomeprazole is an approved medication, and the dose planned for this study, 40 mg qd, is the recommended dose for the treatment of duodenal and gastric ulcers.

While planned study treatments in this study are expected to be well tolerated, routine safety monitoring and in-house stays are included in this study during dosing. Subjects will be asked to report any events of feeling “not well” to study staff immediately.

## 2. OBJECTIVES AND ENDPOINTS

This study will investigate the effect of esomeprazole and the effect of food on the pharmacokinetics of balovaptan in healthy volunteers. Study objectives are presented in [Table 1](#).

**Table 1 Objectives and Corresponding Endpoints**

Objective	Endpoints
Primary Objectives	

 
To investigate the effect of esomeprazole on the PK of balovaptan following a single oral dose of balovaptan in the fasted state
 
To investigate the effect of a high-fat meal compared to the fasted state on the PK of balovaptan following a single oral dose of balovaptan
 
	
 
Plasma concentrations of balovaptan
 
Derived plasma PK parameters for balovaptan
 

Secondary Objectives	

 
To investigate the effect of esomeprazole on the PK of M2 (as appropriate) and M3 following a single oral dose of balovaptan in the fasted state
 
To investigate the effect of a high-fat meal compared to the fasted state on the PK of M2 (as appropriate) and M3 following a single oral dose of balovaptan
 
To measure the PK of esomeprazole following 5 once daily dosing of esomeprazole
 
	
 
Plasma concentrations of M2 and M3
 
Derived plasma PK parameters for M2 and M3
 
Plasma concentrations of esomeprazole
 
Derived plasma PK parameters for esomeprazole
 

Objective	Endpoints

 
To investigate the safety and tolerability of a single 20 mg oral dose of balovaptan alone or in combination with esomeprazole in healthy subjects
 
	
 
Incidence and severity of AEs, incidence of SAEs, nonserious AESIs, and AEs leading to treatment withdrawal
 
Results of vital signs, 12-lead ECGs, physical examinations, and clinical laboratory tests
 

Exploratory Objectives	

 
To explore the effect of genetic variations in genes associated with drug ADME and transport on the PK and/or safety profile of balovaptan.
 
	
 
Genotyping data for study subjects. Data will be reported separately if analysis is conducted
 

ADME=absorption, distribution, metabolism, excretion; AE=adverse event; AESI=adverse event of special interest; ECG=electrocardiogram; PK=pharmacokinetics; SAE=serious adverse event;

### 3. STUDY DESIGN

#### 3.1 DESCRIPTION OF THE STUDY

This will be a single-center, part-randomized, open-label, single-dose, 3-period crossover study to investigate the effect of food and of esomeprazole on the PK of balovaptan in healthy volunteers.

Screening will be conducted between Day -28 and Day -2.

In Period 1, eligible subjects will be admitted to the clinical research unit (CRU) on Day -1 (the day prior to balovaptan dosing on Day 1) and will remain confined in the CRU until discharge on the morning of Day 5.

In Period 2, subjects will be re-admitted to the CRU on Day -1 (the day prior to balovaptan dosing on Day 1) and will remain confined in the CRU until discharge on the morning of Day 5.

In Period 3, subjects will return to the CRU for re-admission 5 days prior to administration of balovaptan (Day 9 of Period 2) to begin esomeprazole dosing. Esomeprazole will be dosed for 6 days: for 4 days prior to co-administration with balovaptan on Day 1 of Period 3, plus an additional dose on Day 2. Subjects will be discharged on Day 5.

In each period, following discharge from the CRU on Day 5, subjects will return to the CRU on Day 7 and Day 9 for further PK sampling.

There will be a washout of at least 12 days and up to 21 days between administrations of balovaptan. Thus, re-admission for Period 2 may be between 3 to 12 days after Day 9 of Period 1, and re-admission for Period 3 will be on Day 9 of Period 2.

Subjects will be randomized to 1 of 2 treatment sequences (ABC or BAC) on Day 1 of Period 1, with the treatments being as follows:

[figure not shown]
- Treatment A: 20 mg balovaptan administered as a single oral dose following consumption of high-fat, high-calorie meal
- Treatment B: 20 mg balovaptan administered as a single oral dose following a  $\geq 10$ -hour fast
- Treatment C: 40 mg esomeprazole administered once daily for 6 days and with a single oral dose of balovaptan 20 mg in the fasted state 1 hour after the fifth esomeprazole dose

During treatment periods 1 and 2, subjects will receive each of Treatment A or B, according to the randomization schedule. All subjects will receive Treatment C in Treatment Period 3.

Subjects will return for a follow-up visit on Day 16  $\pm$  2 of Period 3. Assessments during the study will be conducted according to the schedule of assessments ([Appendix 1](#)).

[Figure 1](#) presents an overview of the study design.

**Figure 1 Study Schema**

### 3.2 END OF STUDY AND LENGTH OF STUDY

The end of this study is defined as the date when the last subject, last observation occurs, or safety follow-up is received from the last subject, whichever occurs later.

The total length of the study, from screening of the first subject to the end of the study, is expected to be approximately 11 weeks. For each enrolled subject the duration of the study from screening to last subject observation will be approximately 6 to 11 weeks.

- Screening: Approximately 4 weeks (Day -28 through Day -2)
- Treatment periods:
  - Treatment Period 1: up to 3 weeks (Day -1 – Day 13, 14, 15, 16, 17, 18, 19, 20, or 21 [12 to 21 day washout between balovaptan administrations])
  - Treatment Period 2: 2 weeks (Day -1 – Day 13)
  - Treatment Period 3: 1.5 weeks (Day -1 – Day 9)
- Follow-up: up to 5 days (Day 16 ± 2 of Period 3) (at least 14 days after the final dose of balovaptan)

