### **Study Design**

This will be a single-center, part-randomized, open-label, single-dose, 3-period crossover study to investigate the effect of food and of esomeprazole on the PK of balovaptan in healthy volunteers.

Screening will be conducted between Day -28 and Day -2.

In Period 1, eligible subjects will be admitted to the clinical research unit (CRU) on Day -1 (the day prior to balovaptan dosing on Day 1) and will remain confined in the CRU until discharge on the morning of Day 5.

In Period 2, subjects will be re-admitted to the CRU on Day -1 (the day prior to balovaptan dosing on Day 1) and will remain confined in the CRU until discharge on the morning of Day 5.

In Period 3, subjects will return to the CRU for re-admission 5 days prior to administration of balovaptan (Day 9 of Period 2) to begin esomeprazole dosing. Esomeprazole will be dosed for 6 days: for 4 days prior to co-administration with balovaptan on Day 1 of Period 3, plus an additional dose on Day 2. Subjects will be discharged on Day 5.

In each period, following discharge from the CRU on Day 5, subjects will return to the CRU on Day 7 and Day 9 for further PK sampling.

There will be a washout of at least 12 days and up to 21 days between administrations of balovaptan. Thus, re-admission for Period 2 may be between 3 to 12 days after Day 9 of Period 1, and readmission for Period 3 will be on Day 9 of Period 2.

Subjects will be randomized to 1 of 2 treatment sequences (ABC or BAC) on Day 1 of Period 1, with the treatments being as follows:

- Treatment A: 20 mg balovaptan administered as a single oral dose following consumption of high-fat, high-calorie meal
- Treatment B: 20 mg balovaptan administered as a single oral dose after a  $\geq 10$ -hour fast
- Treatment C: 40 mg esomeprazole administered once daily for 6 days and with a single dose of balovaptan 20 mg 1 hour after the fifth esomeprazole dose in the fasted state

Subjects will return for a follow-up visit on Day 16  $\pm$  2 of Period 3.

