### **4.3 STUDY TREATMENT AND OTHER TREATMENTS RELEVANT TO THE STUDY DESIGN**

The investigational medicinal products (IMPs) for this study are balovaptan and esomeprazole.

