#### **4.3.2.2 Esomeprazole**

Single doses of esomeprazole 40 mg will be administered alone for 4 days prior to coadministration with balovaptan 20 mg on Day 1 of Period 3, and administered alone on Day 2 of Period 3. When esomeprazole is coadministered with balovaptan, esomeprazole will be administered 1 hour prior to balovaptan in a fasted state. Esomeprazole will be administered with approximately 240 mL of water.

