- Drugs of abuse (including amphetamines [including ecstasy], barbiturates, benzodiazepines, cannabinoids, cocaine, cotinine, opiates, methamphetamines, and methadone) and alcohol will be measured in urine at Screening and day of admission for each treatment period. Further testing may be performed throughout the study to confirm compliance, at the discretion of the Investigator.
- Viral serology: HIV -1 and -2 antibodies, hepatitis B core antibody (anti-HBc), hepatitis C virus antibody at screening; hepatitis B surface antigen and hepatitis B viral DNA will be assessed at screening if anti-HBc is positive
- Pregnancy test: beta-human chorionic gonadotropin (serum pregnancy test) will be performed at screening and day of admission of each treatment period and at follow-up for all female subjects.
- Follicle-stimulating hormone: at screening for postmenopausal women to confirm menopause

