### **4.6.2 Subject Discontinuation from the Study**

Subjects will return to the CRU for a follow-up visit on Day 16 ± 2 of Period 3.

Subjects have the right to voluntarily withdraw from the study at any time for any reason. In addition, the Investigator or designee has the right to withdraw a subject from the study at any time. Reasons for subject discontinuation from the study may include, but are not limited to, the following:

- Subject withdrawal of consent
- Study termination or site closure
- Adverse event
- Loss to follow-up
- Subject noncompliance, defined as failure to comply with protocol requirements as determined by the Investigator, designee or Sponsor

Every effort should be made to obtain a reason for subject discontinuation from the study. The primary reason for withdrawal from the study should be documented on the

appropriate eCRF. Subject requests to be withdrawn from the study must be documented in the source documents and signed by the Investigator (or designee). Subjects who withdraw from the study may be replaced at the discretion of the Investigator or Sponsor.

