## Appendix 1: Schedule of Activities

	Scr	Period 1								Period 2								Period 3								F/U
	D -28 to -2	D -1	D 1	D 2	D 3 & 4	D 5	D 7	D 9	w/o	D -1	D1	D 2	D 3 & 4	D 5	D 7	D 9	D10 to D12	D 13 a	D -1 a	D 1	D 2	D 3 & 4	D 5	D 7	D 9	D16 ±2 or ET
Biochemistry	X	X				X				X				X		X			X				X			X
Urinalysis	X	X																								X
Coagulation	X	X																								X
Urine drug and alcohol screen l	X	X								X					X											
Serology	X																									
Pregnancy test m	X	X								X					X											X
FSH n	X																									
Genotyping sample		X																								
Adverse event monitoring	X	X	X	X	X	X	X	X		X	X	X	X	X	X	X	X	X	X	X	X	X	X	X	X	X

ET=early termination; F/U= follow-up; FSH=follicle-stimulating hormone; w/o=washout

- Day 13 of Period 2 is Day -1 of Period 3.
- Balovaptan will be administered following a high-fat, high-calorie meal (Treatment A) or after a ≥ 10 h fast (Treatments B and C). Subjects should fast for 4 hours after balovaptan administration and refrain from drinking for 1 hour prior to and 1 hour post dose.
- Esomeprazole will be administered 1 hour prior to balovaptan.
- Standardized meals will be provided at approximately 4 and 8 hours post-balovaptan dosing in each treatment period
- Samples at predose, and at 0.25, 0.5, 1, 1.5, 2, 2.5, 3, 3.5, 4, 5, 6, 8, 12, 16, 24, 36, 48, 72, 96, 144, and 192 hours post dose
- Samples at predose, 0.25, 0.5, 1, 1.5, 2, 3, 4, 6, 8 hours post dose of esomeprazole
- Height, weight, and BMI calculation at screening; only weight at all follow-up.
- Safety ECG will be performed in triplicate at Screening and on Day -1 of each period; at all other time points single ECGs will be performed.
- Body temperature and respiratory rate will be measured at Screening and Day -1 of each period only.
- Orthostatic challenge testing will be performed at screening.
- On Day 1, vital signs measurements will be performed at 1 hour post dose.
- Drugs of abuse (amphetamines [including ecstasy], barbiturates, benzodiazepines, cannabinoids, cocaine, cotinine, opiates, methamphetamines, and methadone).
- Serum pregnancy test performed on all female subjects at Screening and Day -1 of each treatment period (Day 13 of Period 2 is Day -1 of Period 3) and at follow-up.
- In postmenopausal women to confirm menopause

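### The follow-up window allows a visit one day short of its own 14-day minimum, and the Period 3 pregnancy test is placed on two different days

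*Combined protocol and SAP*

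**What the plan says.** **Follow-up visit.** Section 3.2 gives a window and a minimum in one line: "Follow-up: up to 5 days (Day 16 ± 2 of Period 3) (at least 14 days after the final dose of balovaptan"). Elsewhere the window stands without the minimum:

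- The synopsis says "Subjects will return for a follow-up visit on Day 16", with ± 2 days in Period 3, and Section 3.1 repeats this.
- Section 4.6.2 says "Subjects will return to the CRU for a follow-up visit on Day 16 ± 2 of Period 3".
- The follow-up column of Appendix 1 is headed with the same window.

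Section 4.6.1 repeats the 14-day minimum for subjects who terminate early. Section 5.3.1 keeps adverse event reporting open for up to 14 days from the last dose of study drug.

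**Pregnancy test in Period 3.** Section 4.5.5 says that the serum test "will be performed at screening and day of admission of each treatment period and at follow-up for all female subjects". Exclusion 2 (synopsis and Section 4.1.2) also refers to a positive test at admission, without naming a period. For Period 3, Section 3.1 describes "re-admission 5 days prior to administration of balovaptan (Day 9 of Period 2) to begin esomeprazole dosing". The pregnancy-test footnote of Appendix 1 instead names Day -1 of every period, and equates Day -1 of Period 3 with Day 13 of Period 2.

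Under Section 4.3.2.2, esomeprazole is "administered alone for 4 days prior to coadministration with balovaptan 20 mg on Day 1 of Period 3". Section 4.3 states: "The investigational medicinal products (IMPs) for this study are balovaptan and esomeprazole".

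**The concern.** The window and the minimum cannot both hold across all five permitted days. A site that schedules from the synopsis, Section 3.1, Section 4.6.2 or Appendix 1 could book Day 14 in good faith and breach Section 3.2. The visit would then also come before adverse event reporting closes, so the last part of that period would have no scheduled contact after it.

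In Periods 1 and 2 admission is on Day -1, so the two descriptions of the pregnancy test agree. Only in Period 3 do they separate. Section 4.6.1 makes pregnancy a reason to stop study treatment permanently, so the test day decides whether a positive result arrives before or after esomeprazole has been started.

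**Working it through.** **1. Day count.** The final balovaptan dose is on Day 1 of Period 3 (Section 3.1). The rule is: days after dose = visit day − 1. The protocol's own figures confirm it in two ways.

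- Balovaptan sampling ends with "72, 96, 144, and 192 hours post dose" (Appendix 1). 96/24 = 4, 144/24 = 6 and 192/24 = 8 days, which are the Day 5, Day 7 and Day 9 samples.
- Re-admission for Period 2 is 3 to 12 days after Day 9, so on Day 12 to Day 21. Dosing is the next day, Day 13 to Day 22. 13 − 1 = 12 and 22 − 1 = 21, which reproduces the stated washout of 12 to 21 days.

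**2. Follow-up window.** 16 − 2 = 14 and 16 + 2 = 18. Days 14 to 18 are five days, which reproduces the five days stated in Section 3.2. Day 14 is therefore deliberately counted in.

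| Follow-up day | Days after balovaptan (day − 1) | At least 14? |
|---|---|---|
| 14 | 13 | No |
| 15 | 14 | Yes |
| 16 | 15 | Yes |
| 17 | 16 | Yes |
| 18 | 17 | Yes |

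**3. Adverse event reporting.** Counted from balovaptan (Day 1), the 14 days end on Day 1 + 14 = Day 15. Counted from the last esomeprazole dose (Day 2), they end on Day 2 + 14 = Day 16. Day 14 precedes the end on either count.

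**4. Period 3 calendar, in Period 2 days.** Day -1 of Period 3 is Day 13 (Appendix 1), so balovaptan dosing on Day 1 of Period 3 is Day 14.

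- Admission five days earlier: 14 − 5 = Day 9, as Section 3.1 states.
- Esomeprazole alone on the four days before: Days 10, 11, 12 and 13. It is then given on Days 1 and 2 of Period 3. 4 + 1 + 1 = 6, which reproduces the stated six days. A first dose on Day 9 would give seven.

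| Test day | Source | Esomeprazole doses on earlier days | Days before balovaptan |
|---|---|---|---|
| Day 9 | Section 4.5.5 with Section 3.1 | 0 of 6 | 14 − 9 = 5 |
| Day 13 | Appendix 1 footnote | 3 of 6 (fourth due that day) | 14 − 13 = 1 |

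The two days are 13 − 9 = 4 days apart. The X marks in the Appendix 1 grid are not used, because column alignment is uncertain in the text as extracted.

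**The case against.** **On follow-up.** The two conditions in Section 3.2 can be met together on any of Days 15 to 18. The nominal Day 16 gives 15 days, and a reader of that line sees the minimum beside the window. All of this is true and keeps the point small. It does not remove the error, because the five-day count includes Day 14 and the other places give the window alone.

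Counting the dosing day as day 1 would rescue Day 14, but it contradicts the sampling hours and the washout. Adverse event reporting has its own rule, and Section 5.6 covers later related serious events. So a Day 14 visit does not by itself breach the reporting rule.

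**On the pregnancy test.** Neither text says that its day is the only one, and testing on both days satisfies both. That stands: this is not a case where obeying one text breaks the other. Sections 3.1 and 4.5.5 also refer to Appendix 1 for timing, but that does not remove the admission-day wording in Section 4.5.5. Exclusion 2 points the same way as Section 4.5.5, though less firmly because it names no period. The footnote alone names Day 13.

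**A wider reading.** A reader might infer the same conflict for the urine drug and alcohol screen, since Section 4.5.5 places it at admission and exclusion 21 refers to Day -1. The documents do not support this. Exclusion 21 is an eligibility criterion, the Appendix 1 footnote for that screen gives no day, no passage names Day 13 for it, and Sections 4.4.4 and 4.5.5 expressly allow extra screens. No text is broken.

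**Conclusion.** Wrong as written, and minor.

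- **Follow-up:** one of five permitted days (Day 14) falls one day short of the 14-day minimum. It also precedes the end of adverse event reporting.
- **Pregnancy test:** the two Period 3 days are four days apart. One falls before any esomeprazole and the other after three of six doses. Both precede the Period 3 balovaptan dose, so only esomeprazole exposure differs. Women are also tested at screening and in Periods 1 and 2.

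The follow-up result assumes that days are counted as in the sampling schedule and that the subject receives balovaptan on Day 1 of Period 3. The pregnancy-test result rests on the footnote's wording.

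A reader might infer that the pharmacokinetic comparison is affected. It is not: balovaptan sampling ends at 192 hours (Day 9), before any follow-up visit, and the position of the pregnancy test changes no sampling time or model term.

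**What to change.** - Reconcile the follow-up window with the 14-day minimum across the synopsis, Sections 3.1, 3.2, 4.6.1 and 4.6.2, and Appendix 1, so that no permitted day breaks the minimum.
- Reconcile the Appendix 1 pregnancy-test footnote with Section 4.5.5 and exclusion 2 (synopsis and Section 4.1.2). State the Period 3 test day or days relative to the first esomeprazole dose.

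The sponsor decides which timings stand. The cost is a few wording corrections in the text, the schedule and its footnotes, with no change to sample size or analysis.

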### **3.3 RATIONALE FOR STUDY DESIGN**

This study is designed to evaluate the effect of food and modification of gastric pH by esomeprazole on the PK of balovaptan, with the highest dose strength of the final formulation of balovaptan that may be used in pivotal studies. The PK parameters of balovaptan administered fasted with or without administration of esomeprazole, a gastric pH modifier, or balovaptan administered following a high-fat, high-calorie meal, will be compared. A crossover design was chosen to allow for within-subject assessments, minimizing the impact of variability across subjects on the planned analyses. An open-label study was considered appropriate because of the objective nature of the PK measures.

